- In keeping with the flexibility of DSMB meeting frequency, made the following edit to Section 6.1: “DSMB meetings to review safety data are scheduled for ~~after approximately 100, 200, 300, and all patients have enrolled as desired by the DSMB, as described in the DSMB charter.~~”
- Protocol version 1.6 expanded changed the windows for surveys at Day 28 and at 6 months. Induced changes to the SAP use the union of the windows and SAP edits are noted:
 - Section 5.4: “Note that while 28-day symptom and quality of life assessments will be considered to be on DayA28, there is an allowed ± 2 day – 2 day/+2 week window for when they occur. Likewise, the 6-month *symptom and* quality of life assessments *for analysis purposes will use* have a ± 2 week – 2 week/+2 month window... Because swabs are intended to be delivered along with study drug, the drug delivery date will be assumed to correspond to swab delivery date, with the first swab to be collected on DayD1. There is likewise a window permitted for the Day 28 swab, *although it is narrower: DayR + 26 to DayR + 30, inclusive.*
 - “Participants may complete surveys late (e.g., slow response by email) or dates may be incorrectly entered that suggest assessments were done early. Additionally,

surveys may be completed one day late by phone. It will be assumed that answers to any survey submitted 1 day before or after the intended day for the survey will be treated as the intended day. For example, if the day 4 and day 5 assessments are each completed by email four days after *DayD1*, it will be assumed that the day 4 responses pertain to *DayD4* and the day 5 responses pertain to *DayD5*. However, surveys submitted more than one day before or after the intended day will not be analyzed (except for baseline surveys, which have a longer window because they may be done any day between randomization and the study treatment delivery, inclusive, and day 28 surveys, which have a $\pm 2\text{ day} - 2\text{ days} / +2\text{ weeks}$ window, and 6 month surveys, with a window of $-2\text{ weeks} / +2\text{ months}$). Swabs will be analyzed based on the collection date reported by the participant, which may not necessarily match the day on the swab label. If multiple swabs from a participant have the same participant-reported collection date but different results, a positive result will supersede a negative result, and a negative result will supersede an invalid or indeterminate result. If collected swab dates are clearly erroneous (e.g., before day of randomization), the associated swabs will be ignored. If the “day 28” a swab was collected within ± 2 days of day 28 *DayR* + 28, or on a day that coincides with any of days 1–14, it will be used regarded as a Day 28 swab; otherwise, it will be treated as missing. It will also be assumed swab specimens were collected on the intended day.” (The final sentence was deleted because it is confusing given the preceding language—it is assumed swabs were collected on the reported day, which is not necessarily the intended day.)

- Section 7.3.4: Deleted the redundancy in “rate of household viral acquisition rates”.
- Section 7.5.2: Corrected subject-verb disagreement to state “Formal statistical *analysis* analyses of adverse events is not planned”.
- References: Corrected two instances of an author surname from “Lwe” to “Löwe”.

Batch of changes for Version 1.4. Other than one inconsequential update on 23 Feb 2022 explicitly noted below, decisions below drafted and preliminarily approved by subset of statistical team 15–16 Feb 2022, approved by statistical team (BB, CO, RH, TG) on or before 23 Feb 2022, and then proposed to study PIs on 23 Feb 2022.

- Cover page: Added approval date for SAP Version 1.3 and creation date for SAP Version 1.4.
- Edited the handling of swabs on a hospitalized day, which affects the primary outcome. Background: The protocol had assumed swabs would not be collected during hospitalization and prescribed last value carried forward (LVCF), explicitly noting that positive swab results would be assumed during hospitalization if the last pre-hospitalization swab were positive. The SAP had noted swabs may not be collected during hospitalization and also specified LVCF imputation. Discussion with the statistical team

after the primary manuscript had been drafted revealed differences of interpretation among the statistical team as to the intent of the protocol (and SAP) language, but with the expectation that results would be qualitatively similar with various reasonable interpretations because of the small percentage of hospitalized participants and given the swab data available from these participants. The statistical team decided after extensive debate that all hospitalized days would be considered as having a positive swab, even if there were no swab or a negative swab on such a day, and considered this consistent with the original intent of the protocol and the convention already in the SAP that on days with mixed swab results, a positive swab would supersede a negative swab. Thus, a hospitalization's assumed positive swab results would supersede any obtained swabs those days. The edits to the SAP are tracked below.

- Section 5.4: ~~Speciaal handling will be required in the primary analysis of shedding duration for periods in which patients are hospitalized because swabs might not be obtained during hospitalizations. In the primary analysis, the last-value-carried-forward imputation approach will be applied during hospitalization, such that continued viral shedding during hospitalization will be assumed for patients whose last pre-hospitalization assessment is positive. A sensitivity analysis is described in Section 7.2.1. The primary outcome was viral-shedding duration over the first two weeks. Because the protocol stipulated that swabs would not be obtained during hospitalizations, and that positive results would be carried forward through hospitalization, swab status was considered positive for all hospital days. Hospitalizations or swabs documented after day 15 (i.e., DayR + 14) were not used for this outcome. Duration was considered to end on the first day of two consecutive negative swabs, allowing days without swab results between two negative swabs, or on the last available swab result if negative. Without negative confirmation, the outcome was considered right-censored on the day of their last positive result or day 15. In a sensitivity analysis, we treated hospitalized patients prior to day 15 without a prior confirmed negative as right-censored on the day of hospital admission or day 15.~~
- Section 7.2: The primary analysis of shedding duration will *consider every hospitalized day as having a positive swab result*. ~~apply a last-observation-carried-forward imputation approach for missing swabs that would have been obtained during hospitalization. See section 5.4. [23 Feb 2022 note: The sentence “See section 5.4.” had been preserved in this description of changes, but removed from Section 7.2 on 15 Feb 2022. This inconsequential discrepancy was unilaterally resolved by BB on 23 Feb 2022, after the statistical team had approved of the other decisions but before sending to the PIs, by adding this sentence back to Section 7.2.]~~
- Section 5.4: Added the following paragraph: “*Also of note is that we assumed all*

1 PREFACE

1.1 Purpose of SAP

This Statistical Analysis Plan (SAP) describes the planned analysis and reporting for the protocol: UTAH One (Understanding Treatment And Health in the Ongoing coroNa Epidemic): A Hydroxychloroquine Outpatient Study; formerly *Hydroxychloroquine for Outpatients with Confirmed COVID-19 (HCQ Trial)*.

The structure and content of this SAP provides sufficient detail to meet the requirements and standards set by the Data Coordinating Center (DCC).

1.2 Auxiliary/Other Documents

The following documents were reviewed in preparation of this SAP:

- Protocol: UTAH One (Understanding Treatment And Health in the Ongoing coroNa Epidemic): A Hydroxychloroquine Outpatient Study.
- Case Report Forms (CRFs) for the UTAH One protocol

The reader of this SAP is encouraged to read the protocol for details on the conduct of this study, and the operational aspects of clinical assessments.

The purpose of this SAP is to outline the planned analyses to be completed for the UTAH One trial. The planned analyses identified in this SAP will be included in future study abstracts and manuscripts. Also, exploratory analyses not necessarily identified in this SAP may be performed. Any post hoc, or unplanned, analyses not explicitly identified in this SAP will be clearly identified as such in any published reports from this study.

It is possible that, due to updates or identification of errors in specific statistical software discussed in this SAP, the exact technical specifications for carrying out a given analysis may be modified. This is considered acceptable as long as the original, prespecified statistical analytic approach is completely followed in the revised technical specifications.

2 STUDY OBJECTIVES AND OUTCOMES

2.1 Study Objectives

2.1.1 Primary Objective

The primary objective of the UTAH One is to assess the efficacy and safety of hydroxychloroquine (HCQ) for reduction of viral shedding and hospitalization in outpatients with confirmed COVID-19.

2.1.2 Primary Outcome(s)

The primary outcome is duration of viral shedding, as defined by days from randomization to the first of two consecutive negative swabs, measured through 14 days after randomization (formally defined in Section 5.4).

2.1.3 Secondary Outcome(s)

Secondary outcomes are:

- Average level of COVID-19-attributable symptoms
- Hospitalization within 14 days of enrollment
- Persistence of viral shedding on day 28
- Adult household contact viral acquisition

The secondary outcomes according to the original protocol included duration of COVID-19-attributable symptoms rather than average level of COVID-19-attributable symptoms. Reflecting the study PIs' desires, it was decided by May 21, 2020 to change this duration outcome to an exploratory outcome and include the average level as a new secondary outcome.

Another secondary outcome in the original protocol was duration of viral shedding, measured on days 1-14 and 28. Because of how similar this is to the primary outcome, this secondary outcome has been changed in the SAP (and since amended in the protocol) to persistence of viral shedding on day 28.

2.1.4 Exploratory Outcome(s)

Exploratory outcomes include, but are not limited to, the following:

- Duration of COVID-19 Symptoms
- Patient-reported instrument measures at baseline, 28 days, and 6 months

- Patient Health Questionnaire 9 (PHQ-9) Total
- Generalized Anxiety Disorder 7-item (GAD 7) Total
- Post-traumatic Stress Disorder Checklist for DSM-5 (PCL-5) Total
- 5-level EuroQol- 5 Dimension (EQ-5D-5L) Visual Analog Scale (VAS) and index measure
- Viral shedding numerical measurements
- Viral shedding at 28 days
- Hospital admissions within 14 days of randomization but prior to day of study drug delivery
- Cumulative mortality at 6 months
- Hospital admission by 6 months

2.1.5 Safety Outcome(s)

In addition to the following list, it should be noted that some of the secondary and exploratory outcomes also pertain to safety but are not necessarily restated here.

- Adverse event(s) by 14 days
- Mortality by 28 days
- Hospital admission by 28 days

3 STUDY DESIGN AND METHODS

3.1 Overall Study Design

The UTAH One Trial is a prospective, placebo-controlled, randomized controlled trial to evaluate the efficacy and safety of hydroxychloroquine for subjects with COVID-19. Individuals are randomized to either the hydroxychloroquine (HCQ) arm or placebo arm. Doses are scheduled for five days. Follow-up is most frequent through Day 15 but also is to occur at Day 28 and at 6 months.

3.2 Method of Treatment Assignment and Randomization

Randomization is stratified by age group and balanced between the two arms using random permuted blocks of size 2 or 4 (block size varies randomly after the initial block). A DCC faculty statistician has generated the sequence using R version 3.6.0 statistical software. The treatment assignments for study subjects are made available via a REDCap database.

3.2.1 Delivery of Randomization and Emergency Backup

Treatment assignment will be provided via a REDCap database. There are no emergency backup plans.

3.2.2 Handling of Incorrect Randomization in Study Analyses and Reports

It is possible that a patient may be randomized into the incorrect age stratum, due to incorrect birthdate information or improper specification of the age group. Assuming that any such occurrences are very occasional, legitimate errors, any such patients will be analyzed in their corrected stratum (i.e., the stratum defined by their true age) rather than in the incorrectly initially assigned stratum in all analyses in all reports. Restated, corrected stratum rather than initially incorrectly assigned randomization stratum is to be used for analyses in this document.

3.3 Treatment Masking (Blinding)

Because of the expedited timeline for implementing this study, it is infeasible to prepare a placebo in such a way that it is indistinguishable from the HCQ doses. However, study staff are not to inform the subject which treatment arm has been assigned to the subject to make this as nearly single-blinded as possible. For the same reason, it is not practical to implement blinding of research coordinators because they may be involved in preparing the kit (containing, among other study materials, study drug) that is delivered to study participants.

3.4 Study Intervention Compliance

Beginning the day after study medication is delivered, subjects are asked to indicate on five days whether or not study medication was administered the previous day and how many pills remain. The number of pills administered is thereby ascertained.

4 STUDY SUBJECTS AND ANALYSIS POPULATIONS

4.1 Eligibility

The inclusion/exclusion criteria for this study are described in the protocol.

4.2 Populations

4.2.1 Screening Population

The screening population (SCREEN) includes all subjects meeting all inclusion criteria who were entered on site screening logs provided to the DCC.

4.2.2 Eligible Population

The eligible population (ELIGIBLE) includes subjects meeting all inclusion criteria and none of the exclusion criteria.

4.2.3 Consented Population

The consented population (CONSENTED) includes all eligible subjects who consent to study participation.

4.2.4 Intention-to-Treat Population

The Intention-to-Treat (ITT) population consists of all enrolled subjects who were randomized before being administered study treatment¹. Subjects are not considered enrolled until they are randomized to a treatment arm, so the day of randomization and day of enrollment are equivalent. Subjects are considered to be in the treatment arm to which they were randomized, regardless of whether or not they received any doses for the assigned arm. This will be the primary population for efficacy analyses.

4.2.6 Per-Protocol Efficacy Population

The Per-Protocol (PP) efficacy population includes all subjects in the dITT population who receive at least 80% of the assigned treatment's pills/tablets. Efficacy analyses will also be repeated on this subpopulation as sensitivity analyses.

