5.0 Study Procedures

5.1 Intake medication review.

Prior to randomization, study personnel and/or clinical pharmacists will review medications being prescribed for patients on study to confirm eligibility. Study personnel will advise patients to contact the study team if any new medications are prescribed during the 5 day treatment course so that the medication may be reviewed for risk of prolonging QTc.

5.2 Cardiac review.

Prior to randomization, study personnel will review if patient has electrocardiograms (ECG) and will verify that prolongation of QTc has not been diagnosed clinically or on ECG.

5.3 Randomization.

After obtaining informed consent, participants will be randomized using variable block sizes stratified by patient age group (age ≤ 44, 45-59, 60-74, 75+ years). The randomization system at the Data Coordinating Center will require entry of patient initials, date of birth and sex. This will assure that patients do not attempt to enroll multiple times in order to secure active drug.

5.4 Study drug.

This is an open label, variable block randomized placebo controlled trial. If a participant is admitted to the hospital at any time during the active treatment period, the clinical team will decide whether or not to continue study drug treatment during hospitalization.

Participants randomized to the HCQ arm will receive HCQ 400mg po BID x 1 day, then 200mg po BID x 4 days³. The drug dose (2.4 gm over 5 days) falls at the lower end of doses proposed in various international trials, but it has proven in vitro efficacy, with a ratio of lung tissue trough concentrations to the EC50 (effective concentration to suppress 50% of viral activity) of >20.³

Those randomized to placebo will receive a placebo to be taken on the same schedule.

5.5 Study Assessments.

Coordinators will obtain baseline information at the time of randomization. This will include review of all medications being prescribed for patients on study. Study personnel will advise patients to contact the study team if any new medications are prescribed during the 5 day treatment course so that the medication may be reviewed for risk of prolonging QTc, or having a drug interaction with HCQ (see Appendix 3).

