7.3 Secondary Outcome(s) Analyses

For each secondary outcome except the adult household contact viral acquisition, the population of interest is the ITT population, with assigned treatment arm used, even if it differs from administered treatment arm. The viral acquisition outcome is further restricted to households with at least two adults for which no other adult besides the index study subject is positive for COVID-19 at baseline.

7.3.1 14-day Hospitalization

The comparison of proportion of patients hospitalized by $DayR+13$ between the randomized hydroxychloroquine and placebo groups will be performed with a two-sided Cochran-Mantel-Haenszel (CMH) test stratifying by the age categories as used for randomization, with 2-sided $\alpha=0.05$. As noted in Section 5.4, in the unlikely event that some patients die within 14 days after randomization without being hospitalized, these patients will be assigned to the hospitalization category in the analysis. Results will be presented as relative risks with 95% confidence intervals within each age stratum, and then pooled across strata. The pooled estimator is the estimator for the principal analysis.

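### The per-protocol analysis of 14-day hospitalization or death can lose its own events, because the 80% pill rule makes no allowance for admission or death

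*SAP*

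**What the plan says.** SAP 4.2.6 builds the PP set from the drug-delivered set (dITT): "The Per-Protocol (PP) efficacy population includes all subjects in the dITT population who receive at least 80% of the assigned" pills. The section names no exception for a course cut short by admission or death. It then commits to using the set: "Efficacy analyses will also be repeated on this subpopulation as sensitivity analyses". SAP 4.2.5, by contrast, makes the dITT repeats optional.

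Five other places bear on the point:

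- **Dosing.** Protocol 5.4: "Participants randomized to the HCQ arm will receive HCQ 400mg po BID x 1 day, then 200mg po BID x 4 days", with placebo on the same schedule.
- **Admission.** Protocol 5.4 says that if a participant is admitted during treatment, "the clinical team will decide whether or not to continue study drug treatment during hospitalization".
- **Outcome.** SAP 5.4 makes hospitalization or death from DayR to DayR+13 a binary secondary outcome.
- **Pill counts.** SAP 3.4 takes them from participant reports on five days. It describes no inpatient source.
- **Main analyses.** SAP 4.2.4 says of the ITT population: "This will be the primary population for efficacy analyses". For secondary outcomes other than household acquisition, SAP 7.3 says that "the population of interest is the ITT population, with assigned treatment arm used".

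**The concern.** Adherence here is measured over the whole course, but the course can be interrupted by the outcome. Someone admitted on dosing day 2 whose drug is stopped has taken every dose due so far and still fails the 80% rule. The PP analysis of hospitalization/death then drops that person, event included.

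If this happens equally in both arms, the PP risks are too low but the comparison stays centred. If it happens more often in one arm, that arm looks better with no drug effect. The documents make unequal stopping possible. SAP 3.3 says of the placebo that "it is infeasible to prepare a placebo in such a way that it is indistinguishable from the HCQ doses" and that coordinators cannot be blinded. Protocol 7.5 words discontinuation for a contraindication in terms of HCQ only. Protocol Appendix 3 has staff discuss stopping study drug when certain medicines are ordered during the five days.

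A real effect of treatment on early admission would be hidden by the same route. A sensitivity analysis is meant to test the ITT result, and this one could contradict it for reasons unrelated to adherence.

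**Working it through.** **1. Where the 80% line falls.** The protocol's total reproduces: 2 × 400 mg + 4 × (2 × 200 mg) = 800 + 1,600 = 2,400 mg, the stated 2.4 g. The threshold is 0.80 × 2,400 = 1,920 mg.

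| End of dosing day | Cumulative mg | Share | 200 mg tablets (assumed strength) |
|---|---|---|---|
| 1 | 800 | 33% | 4 |
| 2 | 1,200 | 50% | 6 |
| 3 | 1,600 | 67% | 8 |
| 4 | 2,000 | 83% | 10 |
| 5 | 2,400 | 100% | 12 |

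80% of 12 tablets is 9.6, so 10 are needed. The tenth is the last dose of day 4. A permanent stop before that dose fails the rule; a later stop does not.

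**2. Selection formula.** Let p be the 14-day risk of admission or death, f the share of those events before the threshold, and s the probability that drug is then stopped or not recorded. The share of events kept is 1 − fs, and

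PP risk = p(1 − fs) / [p(1 − fs) + (1 − p)].

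The documents give none of p, f or s, so every value below is an assumption. If the first dose is on DayR+1 and admissions are uniform over DayR+1 to DayR+13, f = 4/13 = 31%.

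**3. Unequal stopping, true RR 1.00, 80% on HCQ and 40% on placebo.**

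| f | Events kept, HCQ / placebo | Ratio of kept shares | PP RR, p = 5% | PP RR, p = 10% |
|---|---|---|---|---|
| 31% | 0.754 / 0.877 | 0.860 | 0.865 | 0.870 |
| 45% | 0.640 / 0.820 | 0.780 | 0.788 | 0.795 |

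With 100% against 50% stopping and p = 5%, the PP RR is 0.86, 0.68 and 0.41 for f = 25%, 50% and 75%. The direction reverses if placebo is stopped more often.

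**4. Equal stopping, true RR 1.00.** The PP RR stays at 1.00 and only the risks fall. With p = 5%, f = 50% and s = 1 in both arms, 5 of the 10 expected events per 200 are lost, and the risk falls from 5.0% to 0.025/0.975 = 2.6%.

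**5. A real early effect.** Take a placebo risk of 10%, half of it early, HCQ doubling early admissions, and all early events removed. The ITT RR is 0.15/0.10 = 1.50. The PP RR is (0.05/0.90)/(0.05/0.95) = 1.06.

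**6. Primary outcome on the PP set.** Here selection acts through the rule that hospital days count as positive swabs. A 4,000-run log-rank simulation under the null assumed 65% clearance, p = 5% to 10%, f = 50% and 7 hospital days. It gave PP mean hazard ratios of 1.00 to 1.01 and type I error of 4.3% to 5.6%, including with 100% against 0% removal. Simulation error alone gives 5% ± 1.96 × √(0.05 × 0.95/4,000) = 4.3% to 5.7%.

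**The case against.** The main points on the other side:

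- **Admission alone does not remove anyone.** A reader might infer that all early-admitted participants leave the set. Protocol 5.4 allows drug to continue in hospital, so removal also needs a stop, a death or a missing record before the threshold. This stands.
- **Not every PP analysis is affected in this way.** A reader might infer that all the PP efficacy repeats are selected on the outcome. Selection is direct only for hospitalization/death. It was negligible for shedding in the ranges tried, and is at most indirect for symptoms, day-28 shedding and household acquisition. This stands.
- **The PP set is a sensitivity set.** The ITT analyses are untouched, and selection after randomization is a known limit of any adherence-defined set. This stands, but the plan still commits to the analysis, and this part of the selection is avoidable.
- **Unequal stopping is inferred.** The documents do not say that the hospital team knows the assignment. Distinguishable tablets make unequal stopping possible and do not show that it happened.
- **The numbers are small.** With p = 5% and 200 per arm, the 0.86 case is about 7.5 against 8.8 events, with an approximate 95% interval for the RR of 0.33 to 2.25. That is a fair limit on what the analysis can show. It does not justify losing some of its few events.
- **Exclusion reasons are already planned.** SAP 7.1 requires them in the CONSORT-like diagram. Only an explicit breakdown by arm is missing.

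**Conclusion.** The point holds for one analysis, the PP repeat of 14-day hospitalization/death. As SAP 4.2.6 is written, that analysis can lose events because they occurred. It is biased if stopping differs by arm or if treatment changes early admission.

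The size cannot be determined from the documents. Under a true RR of 1.00, the 80% against 40% assumption gives a PP RR of about 0.86 to 0.87 with 31% of admissions early, and 0.78 to 0.80 with 45%. Equal stopping gives 1.00, and drug continued and recorded for everyone gives no selection at all. These figures also assume 200 mg tablets, a first dose on DayR+1 and full adherence until the stop. Protocol 3.3 places typical admission 5 to 7 days after symptom onset, and enrolment is within 72 hours of a positive test. An early share of 31% is therefore not extreme, though it has no source in the documents.

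The documents do not support the wider conclusion that the trial's efficacy results are compromised. The ITT analyses carry those results.

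**What to change.** For the PP analysis of 14-day hospitalization/death, add to SAP 4.2.6 a variant along these lines: *a dITT participant is adherent if at least 80% of the pills scheduled up to the earliest of hospital admission, death or the end of the 5-day course were taken; admission or death alone does not remove a participant.* State where the pill count comes from for participants who are admitted, and how a missing count is handled. Report PP exclusions by arm and reason.

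The SAP's change log for version 1.4 shows that results had already been viewed. The variant should therefore stand beside the existing PP definition and be labelled post hoc, as SAP 1.2 requires for unplanned analyses. It should not replace that definition. It changes no rule about giving or stopping study drug.

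The cost is a short SAP addition and a little extra programming. The variant set is slightly larger and less strict: someone admitted on day 1 after a few tablets would count as adherent, so it answers a somewhat different question. Where participant reports stop at admission, the count may be incomplete.
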